Information pertaining to AEs noted during the study will be listed by patient, including the verbatim term given by the Investigator, the PT and SOC given by the MedDRA dictionary, start and end date, causality, severity, and relationship to study drug as assessed by the Investigator.

BK-polyoma viremia and nephropathy

The following variables will be analyzed descriptively:

- occurrence of BK-polyoma viremia any time post-transplantation “on treatment”
- occurrence of BK-polyoma viremia any time after switching a patient to SoC treatment
- occurrence of BK-polyoma virus nephropathy any time post-transplantation “on treatment”
- occurrence of BK-polyoma viremia any time after switching a patient to SoC treatment.

The difference of the investigational regimens to the control regimen will be summarized by risk ratios and appropriate CIs.

EBV, CMV and TB

All EBV, CMV and TB surveillance data will be listed by treatment, subject, and visit/time and if normal ranges are available, abnormalities will be flagged. Summary statistics will be provided by treatment and visit/time.

Laboratory data

Abnormalities according to clinically notable criteria will be identified. A by-subject listing of individual subject laboratory data will be generated. Values outside of the clinically notable limits will be flagged. Shift tables describing changes from randomization/enrollment based on the clinical notable criteria will be presented.

Descriptive statistics (mean, standard deviation, minimum, median and maximum) of quantitative laboratory variables, including change from randomization/enrollment, will be generated by visit.

New onset diabetes mellitus (NODAT)

The incidence of subjects developing new onset diabetes mellitus after transplantation (NODAT) will be summarized by treatment group. The probabilities of developing NODAT will be compared between treatment groups at 6 and 12 months post-transplant using logistic regression models with HbA1c levels at randomization/enrollment as predictive variables. Death, graft loss, or loss to follow up without NODAT before Month 12 will not be counted as developing NODAT. This analysis will be performed using subjects in the FAS population who do not have DM at randomization/enrollment.

Corporate Confidential Information

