6.1.4 Supportive analyses

Kaplan-Meier estimates

In this analysis, patients who have not experienced tBPAR, will be censored with the censoring time as defined by the last contact day at or before the cut-off point (e.g., 1st IA Month 3 visit, 2nd IA Month 6 visit). The patients will be considered as completed at the date of their corresponding analysis cut-off point. In addition to the Kaplan-Meier plot, a log-rank test shall be performed to obtain estimates with CI's for each treatment arm and the difference between treatment arms.

During data review, it was noticed that some patients were switched from the randomized treatment to another regimen. Therefore in future IA's, more focus shall be placed on the Kaplan-Meier analysis.

Supportive Bayesian analysis

In addition the Bayesian analysis will be repeated with a model using a Poisson distribution to account for the patients that may switch treatment or discontinue early from the study. The following parametrization will be used:

The number of tBPAR events in group i is assumed to follow a Poisson distribution, i.e.

$$y_i = \text{Poisson}(\mu_i),$$

where μ_i is the expected number of events in group i, with

$$\mu_i = \lambda_{i,T} * t_{i,T},$$

with $t_{i,T}$ being the total follow up time in group i (times censored at treatment switch or discontinuation) up to analysis time point T and λ_i being the event rate in group i up to the analysis time point T. For sensitivity analysis of the primary analysis the analysis time point T is week 12 (i.e. week 13 visit, month 3 after transplantation). The probability of an tBPAR event occurring up to the analysis time point can then derived as $\theta_i = 1 - \exp(-\lambda_i * T)$.

The pre-defined success criteria is considered to be a difference in the probability of tBPAR between the CFZ533 arm and the control group of less than 20 percentage points with at least 60% level of proof.

$$\Pr(\theta_{CFZ533} - \theta_{SoC} < 0.20 | \text{data}) > 60\%$$

The required posterior probabilities will be estimated from simulations of the posterior distributions of $\theta_{CFZ533} - \theta_{SoC}$ and compared to the thresholds for the levels of proof.

The prior distributions will be assumed to be a non-informative Beta(1/3,1/3) for θ_{CFZ533} and an informative prior of Beta(1, 13) for θ_{SoC} .

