- AEs leading to discontinuation of a study drug by SOC and PT
- AEs leading to dose adjustment or interruptions of a study drug by SOC and PT
- Infections by type of infection (viral, bacterial, fungal, and others) and microorganism of infection
- Serious infections by type of infection and micro-organism of infection
- New onset diabetes mellitus
- AEs by standardized MedDRA query (SMQ) levels (broad and narrow search)
- AEs by standardized MedDRA query (SMQ) and preferred term (broad and narrow search)

In all tables about incidence rates of AEs / Infections, if a patient has multiple occurrences of an AE, this patient will be counted only once in the corresponding AE category. If a patient has multiple adverse events within a system organ class, s/he will be counted only once for that class. If a patient has multiple severity ratings for an AE while on treatment, s/he is only counted under the maximum rating. In the tables, only adverse events occurring at or after first drug intake are included.

Information pertaining to AEs noted during the study will be listed by patient, including the verbatim term given by the investigator, the PT and SOC given by the MedDRA dictionary, start and end date, causality, severity, and relationship to study drug as assessed by the investigator.

BK-polyoma viremia and nephropathy

The following variables will be summarized by treatment and listed by treatment group and patient:

Occurrence of BK-polyoma viremia any time post-transplantation

Occurrence of BK-polyoma virus nephropathy any time post-transplantation

The difference of the investigational regimens to the control regimen will be summarized by risk ratios and appropriate CIs.

Tuberculosis surveillance

Tuberculosis (TB) test data collected will be listed by patient and visit.

Pregnancy test

Pregnancy test results for all females will be listed by patient and visit.

Desirability of outcome ranking (DOOR)

Composite endpoint:

- a) Survived; without graft loss and without tBPAR
- b) Survived; without graft loss and with tBPAR
- c) Survived; with graft loss and without tBPAR
- d) Survived; with graft loss and with tBPAR
- e) death

Long term renal function:

- a) Normal creatinine; without BK and without tBPAR

- b) Normal creatinine; with BK and without tBPAR
- c) Normal creatinine; without BK and with tBPAR
- d) Normal creatinine; with BK and with tBPAR
- e) Elevated creatinine; without BK and without tBPAR

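### SAP 7.1.2 counts BK viremia and BK nephropathy only over the whole post-transplant period, so its risk ratio cannot separate on-treatment from post-switch events as protocol 9.5.3.2 sets out

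*SAP*

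**What the plan says.** SAP 7.1.2, under the BK-polyoma heading, has two variables: "Occurrence of BK-polyoma viremia any time post-transplantation" and "Occurrence of BK-polyoma virus nephropathy any time post-transplantation". On grouping it says "The following variables will be summarized by treatment and listed by treatment group and patient". On comparison it says "The difference of the investigational regimens to the control regimen will be summarized by risk ratios and appropriate CIs". It sets no on-treatment limit for BK and has no category for time after a switch.

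Protocol 9.5.3.2, under the same heading, has four bullets:

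1. Viremia on treatment: "occurrence of BK-polyoma viremia any time post-transplantation “on treatment" (the bullet ends there).
2. Viremia after a switch: "occurrence of BK-polyoma viremia any time after switching a patient to SoC treatment".
3. Nephropathy: "occurrence of BK-polyoma virus nephropathy any time post-transplantation", again limited to the on-treatment period.
4. The text of bullet 2 again, about viremia.

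The protocol calls the analysis descriptive and closes with the same risk-ratio sentence as the SAP.

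On switching, SAP 6.1.4 reports that "it was noticed that some patients were switched from the randomized treatment to another regimen". Protocol 5.5.10 asks that patients who stop study treatment stay in the study on SoC to Month 12 where possible.

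**The concern.** The SAP says in 1.1 that it implements the analysis planned in the protocol. For BK it does something different from the protocol supplied with it. Protocol 5.5.5 gives BK viremia as its example of over-immunosuppression when CFZ533 is combined with MPA and corticosteroids after basiliximab. Part 2 tests a CNI-free regimen, and patients who leave it go to local SoC. A reader of the BK table will want to know whether an event arose on the assigned regimen or after it was stopped. A single whole-period count does not show this, and the risk ratio built on it inherits the ambiguity. With arms of about 30 and 15, a few events can move the ratio visibly.

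**Working it through.** **Setting the texts side by side**

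| Variable | Protocol 9.5.3.2 | SAP 7.1.2 |
|---|---|---|
| Viremia, on treatment | Listed | Not listed |
| Viremia, after switch | Listed (twice) | Not listed |
| Viremia, any time | Not listed | Listed |
| Nephropathy, on treatment | Listed | Not listed |
| Nephropathy, after switch | Not listed (fourth bullet repeats viremia) | Not listed |
| Nephropathy, any time | Not listed | Listed |

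**Does another rule restore the split?**

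- Protocol 9.5.3 includes post-discontinuation data in safety analyses unless something else is specified. The BK bullets do specify something else, so this default does not support the SAP's choice.
- SAP section 4 analyses patients by treatment actually received when this differs from the randomized arm. It does not reassign events by time, so a patient who starts on one arm and switches later most naturally stays in the starting group. This is an inference; the SAP does not state it.
- SAP 7.1.2 excludes data after a switch for eGFR. No such sentence covers BK.

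**Illustration of sensitivity**

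The documents state no BK rate, BK count or switch rate, so there is no planned figure to reproduce. All event counts below are assumed; only the arm sizes (30 and 15) come from the documents.

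Risk ratio: RR = (a/30)/(c/15), where a and c are patients with an event in the CFZ533 and control arms. One more CFZ533 patient with an event changes RR by (1/30)/(c/15) = 0.5/c. That is 0.50, 0.25 or 0.17 for c = 1, 2 or 3.

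Start from on-treatment counts of 6/30 and 3/15: RR = 0.20/0.20 = 1.00.

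| Post-switch CFZ533 patients added | RR, no control event added | RR, one off-treatment control event added |
|---|---|---|
| 0 | 1.00 | 0.75 |
| 1 | 1.17 | 0.88 |
| 2 | 1.33 | 1.00 |
| 3 | 1.50 | 1.12 |
| 4 | 1.67 | 1.25 |

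The shift can go either way, depending on how many patients leave treatment in each arm.

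A second assumed case uses 3 CFZ533 patients with viremia on treatment, 3 more only after a switch, and 2 control patients, both on treatment:

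- On treatment: (3/30)/(2/15) = 0.75. SE of log RR = √(1/3 − 1/30 + 1/2 − 1/15) = √0.733 = 0.856. The 95% CI is 0.75 × exp(±1.96 × 0.856), about 0.14 to 4.0.
- Any time: (6/30)/(2/15) = 1.50. SE = √(1/6 − 1/30 + 1/2 − 1/15) = √0.567 = 0.753. The 95% CI is about 0.34 to 6.6.

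The point estimate crosses 1, but both intervals are wide and neither establishes a direction.

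**The case against.** A reader might infer that the SAP charges post-switch BK events to CFZ533 and so biases the ratio against it. The documents do not support that. The whole-period count applies to both arms, and SAP 6.1.4 gives neither the arm, the number nor the timing of switches.

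A reader might also infer that the SAP authors removed a split that was in front of them. SAP 1.2 cites protocol v02, and SAP 1.4.1 describes a three-part study, whereas the supplied protocol has two parts. The split may have been added after v02. Only a mismatch between the supplied documents is shown.

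The any-time count has merit. It is a valid treatment-policy summary. Protocol 3.6.1.2 says immune suppression may last weeks to months after CFZ533, so an event after a switch may still reflect it. Protocol 5.5.5 ties biopsy-proven BK nephropathy, and persistent or severe over-immunosuppression, to a switch. The on-treatment cut-off is therefore informative, and an on-treatment ratio alone could understate the burden. This stands, and it is why the any-time row should be kept.

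Timing is also recoverable. SAP 7.1.2 lists BK results by patient and visit, and AE listings carry dates. In about 45 patients a reader could rebuild the split, but that does not replace a prespecified summary.

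Finally, the protocol does not name the on-treatment ratio as the headline, and the visible text of 9.4.1 does not show the on-treatment window. The 0.75 above is one reading, not the protocol's figure.

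**Conclusion.** The point holds as a mismatch between documents with a limited analytic consequence. As written, the SAP's BK risk ratio cannot separate events on assigned treatment from events after a switch, in either arm, whereas the supplied protocol makes that separation for viremia and limits nephropathy to the on-treatment period. The full split is printed only for viremia. The fourth protocol bullet duplicates the second, apparently where nephropathy after a switch was meant.

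Direction and size are unknown, and the ratios shown rest on assumed counts. That switchers stay in their starting group is the natural reading of the SAP, not a stated rule. Severity is low: the table is descriptive, and neither the success criterion nor the stated numerical stopping rules (protocol 9.4.2, 9.6 and Appendix 3; SAP 1.4.3 and 6.1.3) use BK events. At most, BK could enter the case-by-case review of infections in Appendix 3.

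**What to change.** In SAP 7.1.2:

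- Report three variables each for BK viremia and BK nephropathy: on assigned treatment, after a switch to SoC, and any time after transplant.
- State the on-treatment window used for BK.
- Give the on-treatment and any-time risk ratios side by side, labelled as such, with time on treatment by arm, because treatment duration may differ and stopping may be related to BK.
- State that switchers stay in their original group for the any-time count.

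In protocol 9.5.3.2, correct the fourth BK bullet to nephropathy after switching to SoC.

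The cost is a few table rows from data already collected, some SAP wording and a one-line protocol correction. The one drawback is that the on-treatment ratio must be read alongside exposure time and the any-time result, not on its own.

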7.1.3 Graphical presentation

Boxplots to visualize trends in longitudinal safety data (vitals, ECG, lab parameter) will be created.

A figure to represent the desirability of outcome ranking will be created.

Corporate Confidential Information

9 Reference list

